12.5.2.2. Secondary Endpoints

The following secondary efficacy endpoint analyses will be generated on the evaluable set.

Point estimates and two-sided 95% CIs will be presented for the following secondary endpoints:

- PPV and NPV will be computed for the pelvic lymph node packets (one observation per subject for cohort A).
- Sensitivity of ¹⁸F-DCFPyL PET/CT imaging within sites of metastasis or local recurrence relative to histopathology (cohort B)
- PPV will be computed for the biopsies (one observation per subject for cohort B).

The normal approximation to the binomial distribution will be used for endpoints having one observation per subject. The null hypothesis will be rejected for each if the lower limit of the

95% CI exceeds 0.50 for at least 2 of the 3 central readers. Statistics will be computed for each of the three central imaging core lab independent readers.

Lesions per subject, as detected by ¹⁸F-DCFPyL PET/CT and conventional images will be summarized for each tissue type (bone, lymph nodes, soft tissue, and prostate gland) and each of the three central imaging core lab independent readers using evaluable subjects from both cohorts.

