#### 3.2.2 Secondary Efficacy Endpoints

- 1. Sensitivity of F-DCFPyL PET/CT imaging to detect prostate cancer within sites of metastasis or local recurrence relative to histopathology in Cohorts B
- 2. Comparison of detection rates for lesion counts overall and by location (i.e., bone, lymph nodes, soft tissue, prostate gland) between F-DCFPyL PET/CT and conventional imaging in Cohorts A and B combined
- 3. PPV of F-DCFPyL PET/CT imaging to predict prostate cancer within the prostate gland and lymph nodes in Cohort A
- 4. NPV of F-DCFPyL PET/CT imaging to predict the absence of prostate cancer within the prostate gland and lymph nodes in Cohort A
- 5. PPV of F-DCFPyL PET/CT imaging to predict prostate cancer within sites of local recurrence and other metastatic lesions in Cohort B
- 6. Pharmacokinetic parameters derived from blood samples [e.g., Cmax, area under the curve (AUC), total clearance (CL), steady-state volume of distribution (Vss), and mean residence time (MRT)] (subset of Cohorts A and B combined)

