#### 4. STUDY DESIGN

## 4.1. Summary of Study Design

This is an open-label, non-randomized, Phase 2/3, multi-center study designed to evaluate the safety and diagnostic performance of F-DCFPyL PET/CT imaging to determine the presence or absence of metastatic prostate cancer in subjects with high risk prostate cancer who were planned for radical prostatectomy with pelvic lymph node dissection (cohort A), and subjects with radiologic evidence of local recurrence or new or progressive metastatic disease (cohort B) who were biopsied if a positive lesion was found on the F-DCFPyL PET/CT scan. The physician has the option to change the planned protocol specified procedure (i.e., RP ePLND for Cohort A subjects and Biopsy for Cohort B subjects) for the subjects based on the F-DCFPyL PET/CT scan. The details of these changes will be collected on the CRF, and these subjects obviating the planned procedure will not be included in any of the primary or secondary endpoints.

Eligible subjects will be enrolled in a non-randomized, sequential manner, with competitive enrollment between study sites. Ten (10) study sites will be used in the U.S. and Canada.

[figure not shown]
Diagnostic performance characteristics of F-DCFPyL PET/CT imaging will be evaluated using histopathology as the truth standard. Three independent readers from a central imaging core lab will be given access to F-DCFPyL PET/CT imaging, conventional imaging, and biopsy-guided imaging. The central readers will be blinded to all other clinical information (i.e. pathology data) and radiology assessments. Likewise, local pathologists who generate the histopathology results for the primary endpoint are blinded to all imaging results.

A change in clinical management questionnaire will be filled out by an independent urologist who is not otherwise a participant of the study. To maintain the blind for imaging, a statistician who is independent from the PyL study team will generate subject listings. A combination of imaging and clinical data will then be posted to a share point site where the independent urologist will review these data and fill out the questionnaire based on the results he sees prior to PyL imaging and then again after PyL imaging. To keep things simple, only imaging data from reviewer 1 will be presented for this assessment to be performed.

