## 4.2. Definition of Study Drugs and Treatment Follow-up

All subjects will be administered  $9 \pm 1$  mCi  $(333 \pm 37 \text{ MBq})^{18}\text{F-DCFPyL}$  injection followed by PET/CT imaging and either a biopsy or prostatectomy and lymphadenectomy as illustrated in the white boxes in Figure 1. These are the protocol's planned procedures. If a Physician decides to change these planned procedures after PET/CT imaging is obtained, subjects in Cohort A would not have surgery and subjects in Cohort B would not have a conventional imaging guided biopsy. These changes in planned protocol procedures are listed in the shaded boxes below. This should be a small number of subjects who will not be included in the primary analysis of the primary endpoint or any of the secondary endpoints.

Figure 1: Study Schema

If the subject did not want to go through with this planned procedure or withdrew from the study then this would not constitute a change in planned protocol procedure. If the planned procedure was intended but could not be completed, then this is also not a change in planned procedure.

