#### 5.4.6. PK Blood Set

Subjects who provide at least six of the nine scheduled blood samples.

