## 7.7. Analysis of Secondary Efficacy Endpoints

Analysis of secondary efficacy endpoints will be conducted regardless of the outcomes of the primary analyses. Diagnostic testing and imaging detection rates will be analyzed for the evaluable set. The PK parameters will be summarized for the PK blood set.

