#### 7.7.3. Detection Rates for Lesion Counts in both Cohorts Combined

For subjects in Cohort A and B combined, the sum of the lesions per tissue type and overall per subject will be summarized showing the N, mean, median, standard deviation, minimum and maximum values for each central imaging core lab reader including the reader of conventional scans. F-DCFPyL images and conventional images will be summarized separately and the mean of each reader's results from F-DCFPyL PET/CT will be compared to conventional imaging using a one-way repeated measures ANOVA. If the assumptions are not met for this test (see Section 7.2), then a Friedman's test will be performed to determine if there is a difference between any of the groups. If significant is determined from either the ANOVA or the Friedman's test, then a Dunnett's test will be performed to show where the difference exists between each reviewer and the conventional scan. A p-value and 95% confidence interval for the difference in means will be presented for each F-DCFPyL PET/CT reviewer versus conventional imaging. This analysis will be performed on the Evaluable Set.

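### The PET-versus-conventional lesion-count comparison needs only image reads, yet it is restricted to subjects with a procedure and histology, so inclusion depends partly on the PET result

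*SAP*

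**What the plan says.** SAP 3.2.2 lists as secondary endpoint 2: "Comparison of detection rates for lesion counts overall and by location", PET/CT against conventional imaging, both cohorts combined. SAP 5.5.8 builds each count by summing central readers' lesion counts by tissue type and overall, for each image type. Histology does not enter.

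The analysis set is stated three times. SAP 7.7: "Diagnostic testing and imaging detection rates will be analyzed for the evaluable set". SAP 7.7.3: "This analysis will be performed on the Evaluable Set". Protocol 12.5.2.2 summarises the counts for "each of the three central imaging core lab independent readers using evaluable subjects from both cohorts".

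SAP 5.4.3 admits a Cohort A subject only with a prostatectomy or lymphadenectomy and a histopathology result. It admits a Cohort B subject only with a conventional-image-guided biopsy, a histopathology result and a conventional image confirming the site.

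SAP 4.1 lets the physician change the planned procedure on the strength of the PET/CT scan and says that "these subjects obviating the planned procedure will not be included in any of the primary or secondary endpoints". SAP 4.2 expects this to be a small number of subjects "who will not be included in the primary analysis of the primary endpoint or any of the secondary endpoints". It adds that refusal, withdrawal, or an intended procedure that could not be completed is not a change in planned procedure.

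**The concern.** A comparison of two sets of image reads does not need a truth standard. Requiring one here removes subjects for a reason unrelated to whether the endpoint can be measured. Some of that removal follows from the PET scan: the procedure was planned before PET and dropped after it. Whether PET shows something the earlier work-up did not is plausibly related to the within-subject difference being tested.

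SAP 7.7.3 attaches a p-value and a 95% confidence interval to each PET reader's difference from conventional imaging. If changed-procedure subjects differ systematically from the rest, each estimate describes a PET-filtered subset instead of the imaged population. The two cohorts could pull in opposite directions, and the analysis pools them.

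**Working it through.** **Does the plan give a figure to reproduce?** Not for this comparison: there is no expected difference, SD, power or rate of changed procedures. The nearest figure is the Cohort A allowance in SAP 4.3, where 236 evaluable subjects with 10% drop-out or non-evaluable gives 236/0.9 = 262.2, stated as 262. That 10% covers all causes in Cohort A. It is not a rate of PET-driven changes.

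**Do the images precede the procedure?** Yes. Conventional imaging is done at screening or taken from the 6 weeks (Cohort A) or 4 weeks (Cohort B) before Day 1. PET is 1–2 hours after dosing. Surgery or biopsy is at least 12 hours after dosing (Protocol Table 3 and its footnotes).

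**Are reads likely to exist for excluded subjects?** Protocol 10.1.2, 10.1.3 and 10.2 send PET and conventional images to the core lab for all cohorts. SAP 5.5.7.4 and 7.8 use PET lesion counts, reader by reader, in the changed-procedure subjects. SAP Table 4 plans an imaging summary on the Safety Set (14.2.3-11). Availability is a reasonable inference, but it is not stated outright.

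**Is the restriction offset elsewhere?** No. SAP 7.6.2 covers only the primary endpoints, SAP 5.6.1 rules out imputation, and no PET-versus-conventional test is attached to Table 14.2.3-11. The Change in Planned Protocol Procedure Set is used only for an exploratory PPV.

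**Form of the error.** For any one PET reader:

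- all-subject mean difference = (1 − f) × dE + f × dC
- error of the planned estimate = dE − [(1 − f) × dE + f × dC] = f × (dE − dC)

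This is zero only if f = 0 or dC = dE. Exclusions unrelated to the difference, such as refusals, contribute nothing on average.

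**Illustration.** All inputs are assumed: dE = 1.0 lesion; f = 2%, 5%, 10%, which is about 8, 19 and 38 of 377 dosed. Each cell gives the all-subject mean, then (dE − mean)/mean.

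| f | dC = 0 | dC = 1 | dC = 3 | dC = 5 |
|---|---|---|---|---|
| 2% | 0.98, +2% | 1.00, 0% | 1.04, −4% | 1.08, −7% |
| 5% | 0.95, +5% | 1.00, 0% | 1.10, −9% | 1.20, −17% |
| 10% | 0.90, +11% | 1.00, 0% | 1.20, −17% | 1.40, −29% |

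Worked cell: f = 10%, dC = 5 gives 0.9 × 1.0 + 0.1 × 5 = 1.40, and (1.0 − 1.40)/1.40 = −29%. The 10% row treats the plan's whole Cohort A non-evaluable allowance, extended to both cohorts, as PET-driven, so it is a generous upper value.

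**The case against.** The strongest defence is that one prespecified set for all imaging endpoints is a legitimate choice on which protocol and SAP agree. The endpoint is secondary, with no power calculation or success criterion, and the SAP expects few changes. Excluded subjects also remain visible: Safety Set tables of imaging results and procedures (14.2.3-11, 14.2.3-13) and a listing of exclusions from the Evaluable Set (16.2.3-1) are planned. Agreement, low stakes and partial visibility all stand. They limit the importance of the point, but none supplies the paired comparison in all imaged subjects.

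Three stronger readings are tempting, and the documents do not support them.

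- A reader might infer that the sample is selected on the very difference being measured. Exclusion follows a treating physician's decision, whereas the endpoint uses blinded central reads. The two are plausibly correlated but not identical. A Cohort A subject who still has surgery and histology stays in, even if PET altered its extent.
- A reader might infer a direction. Extra PET lesions cancelling surgery in Cohort A would shrink the PET gain. Losing PET-negative Cohort B subjects would enlarge it, and SAP 4.1's description of biopsy following a positive PET lesion hints at that. However, the Cohort B changes set out in SAP 5.5.7.4 involve prostate or lymph-node histology with no biopsy done, and the defining figure is not available here. The net sign is open.
- A reader might infer that PK loses subjects too. Read literally, SAP 4.1/4.2 would do that, but the specific text governs: the PK Blood Set is "Subjects who provide at least six of the nine scheduled blood samples", SAP 5.4.7 defines the urine set likewise, and SAP 7.7, 7.7.4 and 9.1 analyse PK on those sets. This is a wording tension, not a loss of data.

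**Conclusion.** The mismatch between endpoint and analysis set is clear from the text: an image-only comparison is confined to subjects with a procedure and histology, and subjects with PET-triggered changes are expressly removed. Inclusion therefore depends partly on the PET result, and no planned analysis corrects for it.

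The consequence is less certain. The error is f × (dE − dC), and the documents give none of its three terms. The range from 29% too low to 11% too high rests wholly on the assumed values. It shows that even a small excluded share can matter if its mean difference is far from the rest; it does not estimate the actual bias. Sensitivity and specificity in Cohort A, and so the primary conclusion, are untouched.

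**What to change.** In SAP 7.7 and 7.7.3 and Protocol 12.5.2.2, run the lesion-count comparison on all dosed subjects who have both a central PET read and a central conventional read, whatever procedure followed. Keep the Evaluable Set version as a supportive analysis.

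In SAP 4.1 and 4.2, limit the exclusion of changed-procedure subjects to the endpoints that need histology: sensitivity, specificity, PPV and NPV. For PK, this only brings the general sentences into line with the sample-based sets already specified.

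The cost is a wording change and one additional table, provided the core lab has read both image types for all dosed subjects, which should be confirmed. The drawback is that this endpoint will have a different N from the histology-based ones: up to 377, against about 339 (377 × 0.9) if the Cohort A 10% allowance applied to both cohorts. A footnote can explain the difference.

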#### 7.7.4. PK

Blood, plasma, and urine collection at each nominal time will be collected twice per patient. The mean of the values at each nominal time will be used in the creation of parameters used in the analysis. For each subject, blood concentration-time data using actual blood draw times rather than nominal times will be computed by non-compartmental analysis and pharmacokinetic parameters will be generated. Additional blood concentration-time data will be fitted into a two-compartment model to calculate  $T_{1/2\text{-alpha}}$  and  $T_{1/2\text{-beta}}$ . Summary statistics for blood will be presented for maximum concentration ( $C_{max}$ ), area under the (activity-time) curve (AUC), body weight normalized clearance (CL), volume of distribution at steady-state ( $V_{ss}$ ), time to maximum concentration ( $T_{max}$ ), half-life( $T_{1/2}$ ) [noncompartmental analysis],  $T_{1/2}$ -alpha and  $T_{1/2}$ -beta [2-

compartment modelling], and mean residence time (MRT). Since there are two values collected per nominal time, the mean of these values within nominal time will be derived prior to generating the PK parameters. These PK parameters will be derived by an external analyst then summarized for the PK blood set. PSA groups, eGFR groups and eGFR will also be summarized for the PK blood set.

Summary statistics for urinary excretion will be presented for Tmax, Rate max, Rate last, T1/2elim, and Cumulative Urine Recovery. For % of injected dose recovered per each urine collection interval per subject will be used to calculate Tmax, Rate max, Rate last, T1/2elim, and cumulative urine recovery by 4 and 8 hours post-administration if feasible. These PK parameters will be derived by an external analyst then summarized for the PK urine set. eGFR groups as defined in Section 5.5.16 and eGFR will also be summarized for the PK urine set.

The ratio of plasma-to-blood concentrations will be calculated per subject/time-point.

#### 7.8. Analysis of Exploratory Endpoints

Sensitivity and specificity of the prostate gland as well as  $SUV_{max}$ ,  $SUV_{peak}$  and  $SUV_r$  will all be analyzed on the evaluable set. Change in Management defined from the questionnaire will be summarized on the safety set. The PPV endpoint will be analyzed on the Change in Planned Protocol Procedure Set.

- SUVmax, SUVpeak, SUVmean, and volume will be summarized for each tissue location (bone, lymph nodes, soft tissue, and prostate gland) and each of the 3 central imaging core lab independent readers using the evaluable set from both cohorts. SUVr will be summarized in the same manner including a reference lesion also. A 95% confidence interval for the mean or distribution will be presented for each reader based on the assumption on normality defined in Section 7.2.
- Differences in the average across all 3 reviewers for SUVmax, SUVpeak, SUVr, SUVmean, and volume will be compared between histology outcomes using a t-test that assumes unequal variances. If the assumptions for the t-test are not met then a Wilcoxon rank sum test will be performed with corresponding exact 95% confidence intervals defined in section 7.2.
- The average SUVmax, SUVpeak, SUVr, SUVmean, and volume values across all reviewers will be compared between Gleason Score groups at time of radical prostatectomy, Baseline PSA groups and testosterone groups split at the median value. The comparisons of means between groups will be performed using a generalized linear model. If normality cannot be assumed then a Kruskal-Wallis test will be performed instead. Within each group a 95% confidence interval will be presented.
- Point estimates and two-sided 95% CIs for Specificity and Sensitivity will be computed from the prostate gland for Cohort A in the Evaluable Set. The normal approximation to the binomial distribution is planned assuming a null hypothesis of 0.5. If the assumptions are not met then confidence intervals derived from an Agresti-Coull exact test will be used (See Section 7.2). Results will be computed for each of the 3 central imaging core lab independent readers.

- Clinical management questions pre- and post F-DCFPyL PET/CT imaging will be summarized from the questionnaire evaluated by a central reader. The proportion of subjects in Cohort A who had a change in intended clinical management plan from pre-to post PyL scans will be analyzed using a one sample binomial test.
- Point estimates and two-sided 95% CIs for PPV will be computed for the change of management set. An Agresti-Coull 95% confidence interval will be used will be used assuming a null hypothesis of 0.5. Results will be computed for each of the 3 central imaging core lab independent readers.

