5.3. Exploratory Endpoints

- 1. ¹⁸F-DCFPyL uptake in different lesion locations (i.e., bone, lymph nodes, soft tissue, prostate gland) as defined by SUV_{peak}, SUV_{max}, SUV_r results derived from central readers, compared to histopathology (cohorts A and B)
- 2. To assess the relationship between SUV_{peak}, SUV_{max} and SUVr in prostatic and extraprostatic lesions with each of the following: baseline PSA, baseline testosterone level, and Gleason Score at time of radical prostatectomy
- 3. Sensitivity and specificity of ¹⁸F-DCFPyL PET/CT imaging to detect prostate cancer within the prostate gland relative to histopathology (cohort A)
- 4. Changes to clinical management plan based on a review of clinical and radiographic subject data before and after ¹⁸F-DCFPyL PET/CT imaging by a central panel of disease experts using a structured questionnaire

5. PPV of ¹⁸F-DCFPyL PET/CT imaging in subjects with corresponding histopathology that is outside the planned protocol surgical template or biopsy site

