12.5.2.3. Exploratory Analyses

Analyses will be generated on the evaluable set for the following exploratory endpoints:

- The number of lesions per subject will be plotted against baseline PSA and baseline testosterone for each of the three central imaging core lab independent readers using evaluable subjects from both cohorts.
- SUV_{max}, SUV_{peak} and SUVr will be summarized for each tissue type (e.g., bone, lymph nodes, soft tissue, and prostate gland) and each of the three central imaging core lab independent readers using evaluable subjects from both cohorts. The relationship between SUVr in prostatic lesions and baseline PSA and testosterone levels, and Gleason score at time of radical prostatectomy will be evaluated.
- Sensitivity, SUV_{max}, SUV_{peak}, and SUV_r will be computed for the following subgroups in Cohort A:
 - Previous radiation therapy (yes/no)
 - Previous hormonal therapy (yes/no)
 - Previous chemotherapy (yes/no)
- SUV_{max}, SUV_{peak}, and SUV_r will be summarized with positive and negative histopathology. Each will be summarized by Gleason score for the single or dominant prostate tumor nodule.
- The clinical management plans before and after review of ¹⁸F-DCFPyL PET/CT scans will be summarized.

An exploratory analysis of PPV of ¹⁸F-DCFPyL PET/CT imaging in subjects who are excluded from the *evaluable set* but have corresponding histopathology outside the planned protocol procedure will be performed on the *safety set*.

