#### 3.2.3 Exploratory Efficacy Endpoints

- 1. F-DCFPyL uptake in different lesion locations as defined by SUVpeak, SUVmax, and SUVr results derived from central readers for cohorts A and B combined and compared between histology outcomes
- 2. To assess the relationship between SUVpeak, SUVmax, volume, and SUVr and Gleason Score at time of radical prostatectomy, baseline PSA, and testosterone levels for both cohorts
- 3. Sensitivity of F-DCFPyL PET/CT imaging within the prostate gland relative to histopathology in Cohort A
- 4. Specificity of F-DCFPyL PET/CT imaging within the prostate gland relative to histopathology in Cohort A
- 5. Changes to clinical management based on a review of clinical and radiographic subject data before and after F-DCFPyL PET/CT imaging by a central panel of disease experts using a structured questionnaire (Cohort A only)
- 6. PPV of F-DCFPyL PET/CT imaging in subjects with corresponding histopathology for subjects who had a change in the planned protocol procedure (Both Cohorts combined)

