#### **5.5.13. PSA groups**

PSA will be categorized into the following groups:

<0.2 ng/mL
0.2 to <4.0 ng/mL
4 to <20.0 ng/mL
20.0 to <50.0
ng/mL
≥50 ng/mL

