#### 7. EFFICACY

#### 7.1. General Considerations

Statistical tests and their corresponding confidence intervals will be two-sided at the 0.05 significance level.

The estimation of sensitivity and specificity rely on the central imaging core lab independent readers. Each reader's assessments will be summarized separately.

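### SAP 7.8 examines the relation of uptake to PSA, testosterone and Gleason score only by comparing groups, with no slope, correlation or trend test planned

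*SAP*

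**What the plan says.** Protocol 5.3 sets the aim as the relationship of SUV measures, in prostatic and extraprostatic lesions, with "baseline PSA, baseline testosterone level, and Gleason Score". SAP 3.2.3 restates it, adding lesion volume: "and SUVr and Gleason Score at time of radical prostatectomy, baseline PSA, and testosterone levels for both cohorts". Protocol 12.5.2.3 names no method: "The relationship between SUVr in prostatic lesions and baseline PSA and testosterone levels, and Gleason score at time of radical prostatectomy will be evaluated".

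SAP 7.8 supplies the method. Uptake and volume, averaged over readers, are compared between Gleason groups, "Baseline PSA groups and testosterone groups split at the median value". SAP 5.5.13 defines the bands ("PSA will be categorized into the following groups"): below 0.2, 0.2 to <4, 4 to <20, 20 to <50, and 50 ng/mL or more. The test is stated as "The comparisons of means between groups will be performed using a generalized linear model", with the fallback "If normality cannot be assumed then a Kruskal-Wallis test will be performed instead". A 95% CI is given within each group, and Tables 14.2.3-4 to 14.2.3-6 display the results.

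Neither document plans a correlation, a trend test or a regression on the continuous value for this endpoint. SAP Section 10 also drops the protocol's plots of lesion count against PSA and testosterone.

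**The concern.** PSA and total testosterone are collected as numeric laboratory values (Protocol 11.1.5.1), and the endpoint asks about a relationship. Three things follow from the chosen analysis.

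- A comparison of five PSA bands asks whether any band differs from any other. It makes no use of the order of the bands. The same holds for the ordered Gleason totals in SAP 5.5.14.
- The testosterone cut is whatever the sample median turns out to be. Values just either side of it are treated as different, and values far apart on the same side as alike. Because the cut moves with the sample, the result is hard to set beside another study.
- The group displays show a pattern, but no slope or correlation with an interval is produced to summarise it.

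At stake are the precision and readability of an exploratory result, not an efficacy claim.

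**Working it through.** **The plan's own figure.** The documents give no power, expected correlation or PSA or testosterone distribution for this analysis. The only sample-size calculation is for the Cohort A co-primary endpoints (SAP 4.3), and it reproduces. The formula gives 47.09 positive subjects for sensitivity 0.40 against 0.60; 47.09/0.20 = 235.5, so 236 evaluable; 236/0.90 = 262.2, about 262 dosed. I use N=236 only to translate power into a correlation. Adding Cohort B at an assumed 10% loss gives 236 + 0.9 × 115 = 339.5, about 340.

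**Inputs.** Two-sided 5% tests (SAP 7.1: "Statistical tests and their corresponding confidence intervals will be two-sided at the 0.05 significance level"); two testosterone groups, so 1 df; five PSA groups, so 4 df. Assumed: a relation that is linear on the scale analysed; a normally distributed predictor; for PSA, either five equal groups or the SAP's cut points applied to log-normal PSA with median 8–15 ng/mL and log-SD 1.0–1.8.

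**Method.** A continuous 1-df test with power P has noncentrality λ = (1.960 + z_P)². Grouping keeps a share r of the predictor's variance, so the grouped test has noncentrality λ × r, referred to chi-square on its own df.

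**At 80% reference power.** λ = (1.960 + 0.842)² = 7.85. By Fisher's z this is a correlation of tanh(2.802/√233) = 0.18 at N=236, or tanh(2.802/√337) = 0.15 at N=340.

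- Testosterone: r = 2/π = 0.637; 7.85 × 0.637 = 5.00; power on 1 df is 60.8%. Relative loss 1 − 60.8/80 = 24%.
- PSA: r = 0.829 to 0.897; noncentrality 6.51 to 7.04; power on 4 df is 50.6% to 54.3%. Relative loss 37% to 32%.
- PSA, same bands, 1-df ordered trend: 72.3% to 75.6%. Banding alone therefore costs 4.4 to 7.7 points (80 − 75.6, 80 − 72.3), and ignoring order a further 21.3 to 21.7 (75.6 − 54.3, 72.3 − 50.6).
- If the lowest PSA band is empty (3 df), the loss is 27–31%.

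**Range over reference power.**

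| Continuous test | Testosterone split (relative loss) | Five PSA bands (relative loss) |
|---|---|---|
| 50% | 34.6% (31%) | 25.8–27.8% (44–48%) |
| 80% | 60.8% (24%) | 50.6–54.3% (32–37%) |
| 90% | 73.4% (18%) | 64.7–68.7% (24–28%) |
| 95% | 82.0% (14%) | 75.2–78.9% (17–21%) |
| 99% | 92.8% (6%) | 89.6–92.0% (7–9%) |

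**Simulation check** (600 data sets per setting, Monte Carlo error about 0.02; N=236, correlation 0.18; PSA median 10, log-SD 1.5). Pearson 0.797, Spearman 0.748; five-group ANOVA 0.542, Kruskal-Wallis 0.492; median-split t-test 0.602, Kruskal-Wallis 0.580. Comparing like with like, the PSA loss is 32% (0.542/0.797) to 34% (0.492/0.748), and the testosterone loss 24% (0.602/0.797) to 22% (0.580/0.748). At correlation 0.30, continuous power is 0.995 against 0.963 (five-group ANOVA) and 0.955 (median-split t-test); at 0.40 every test reaches at least 0.997.

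**Two sensitivities.** If the relation is linear in log PSA, a straight line in raw PSA keeps only 27–58% of the information, against 83–88% for the SAP's bands. So a continuous analysis helps only on a suitable scale or by ranks. If 10–30% of subjects have suppressed testosterone (assumed), the median-split loss at 80% reference power ranges from 22% to 54%, depending on the share and the scale.

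No magnitude was calculated for Gleason score.

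**The case against.** The strongest reply is that this is an exploratory, unpowered endpoint. The protocol fixes no method, so the SAP contradicts nothing, and the raw values remain available for a later correlation. That stands, and it limits the weight of the point.

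Four stronger readings are tempting, and the documents do not support them.

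- *The plan throws away a fixed quarter to a third of its power.* That figure belongs to a reference power near 80%. With no stated correlation, the loss could be under 10% or close to half.
- *The analysis gives no size or direction.* SAP 7.8 gives a 95% CI within each group, and SAP 7.2.2 provides an exact CI for the difference between two groups when normality fails. Direction and rough size can be read from these. Only a single summary of association is missing.
- *The testosterone test ignores order.* Two groups have no order to lose; the cost there is the median split alone.
- *The loss belongs only to the Kruskal-Wallis fallback.* The planned comparison of means loses about as much (32% against 34% for PSA in the simulation). A generalized linear model could carry an ordered score, but the text specifies a comparison of group means and names no trend term.

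A fair objection to a simple remedy is that pooling could mislead. Only Cohort A excludes prior androgen deprivation (Protocol 7.2), so a pooled correlation with testosterone might reflect cohort rather than uptake. The fix has to deal with this.

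**Conclusion.** The point holds as a modest improvement. The planned group comparisons do not give a direct summary of the relationship the endpoint names, and they use the data less efficiently than a rank or log-scale analysis would. Under the stated assumptions, and if a continuous test had 80% power, the relative loss is about 24% for testosterone and 32–37% for PSA. It is larger for weaker relations and negligible for strong ones. These figures rest on an assumed correlation, assumed distributions and a relation that is linear on the analysed scale; none of these is in the documents. A reader might infer that the trial's efficacy findings are weakened, but no primary or secondary endpoint uses this analysis.

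**What to change.** In SAP 7.8, make the main analysis of this exploratory endpoint either a Spearman correlation with 95% CI, or a regression of log uptake on log PSA and log testosterone as continuous variables. Run it by cohort or with a cohort term, and say which; SAP 3.2.3 refers to both cohorts, while SAP 5.1 says efficacy tables are produced by cohort. Use an ordered-trend test for Gleason total. Keep Tables 14.2.3-4 to 14.2.3-6, with their within-group intervals, as description.

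The cost is a few lines of SAP text and minor programming, with no new data. Specifying it before database lock also avoids choosing the method after seeing the results.
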